### **6.7.3. Laboratory Evaluations**

Data for the following hematology, clinical chemistry, routine urinalysis, pregnancy testing, other screening tests, and other tests analytes received from the central laboratory are to be measured at the scheduled timepoints (Baseline, Week 4, 8, 12, 16, 20, 24, 32, 36, 40, 52 and 59).

In accordance with the baseline value definition in Section 5.1.2, the change from baseline will be derived as follows:

Change (unit) = (post-baseline value – baseline value)

All laboratory data will be reported in SI units. All quantitative laboratory test values at each assessed timepoints will be compared with the relevant reference range in SI units and categorized as:

- Low: Below the lower limit of the reference range.
- Normal: Within the reference range (upper and lower limits included).
- High: Above the upper limit of the reference range.

For summaries which present the worst value with respect to the reference range at the subject level, low and high are each chosen in preference to normal values. For parameters with both

low and high reference ranges, subjects who have assessments within both low and high ranges will be counted within each category for worst value summary tables.

For analysis purposes, values preceded by a “<” or a “>” sign (i.e. those below or above the limits of quantification) will be considered equal to the lower or upper limit of quantification, respectively.

Laboratory values will be assigned toxicity grades, when available, using criteria based on the National Cancer Institute – Common Terminology Criteria for Adverse Events (NCI CTCAE) version 5.0 or higher scale.

For those parameters which are graded with two toxicities such as potassium (hypokalemia/hyperkalemia), the toxicities will be summarized separately. Low direction toxicity (e.g., hypokalemia) grades at baseline and post baseline will be set to 0 when the variables are derived for summarizing high direction toxicity (e.g., hyperkalemia), and vice versa.

Laboratory data will be summarized by default descriptive summary statistics for continuous and categorical variables for the Safety Analysis Set:

- Observed values and change from baseline at each assessed timepoint for each standard continuous laboratory parameter
- Number and percentage of subjects with categorized shift (low, normal, and high) values relative to the reference range at baseline compared to each post-baseline timepoint for hematology and clinical chemistry
- Number and percentage of subjects with worst categorized (low, normal, and high) values relative to the reference range
- Number and percentage of subjects with NCI-CTCAE Grade 1, 2, 3, 4, 3/4, and any grade during post-baseline
- Number and percentage of subjects with categorized shift NCI-CTCAE toxicity values at baseline compared to worst post-baseline result

Listings of all clinical laboratory data including derived change from baseline will be provided for the Safety Analysis Set. Within each listing, laboratory values outside the normal ranges will be flagged as either high or low.

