9.3. Statistical Analyses

9.3.1. General Considerations

All data collected will be summarized by planned timepoint without imputation. Continuous data will be summarized with count, mean, Q1, median, Q3, standard deviation, minimum, and maximum. Change from baseline will additionally include standard error. Categorical data will be summarized with count and percent. Time to event data will be summarized with product-limit estimators of median and quartiles.

All hypothesis tests will be reported with 2-sided *p*-values. Comparison of QW dosing to placebo will use only subjects assigned to receive izokibep 160 mg QW or placebo; comparison of Q2W dosing to placebo will use only subjects assigned to receive izokibep 160 mg Q2W or placebo; comparison of Q4W izokibep to placebo will use only subjects assigned to receive izokibep 80 mg Q4W or placebo. All confidence intervals will be 2-sided with nominal 95% coverage.

Data will be summarized by planned timepoint, using data collected at the visit. Study day will be calculated as postbaseline date minus randomization date, plus 1 (except that study day for pre-randomization dates will not include the plus 1). Day range windows will not be applied for summaries (but may be applied for protocol deviations). Baseline values will be the last value collected before randomization and change from baseline will be calculated as postbaseline value minus baseline value.

Stratified tests will use the strata of prior TNFi use (Yes/No) and enthesitis at baseline (LEI = 0 versus > 0) from the randomization process. If a subject is incorrectly classified into a stratum during the randomization process, the analysis will use the correct classification, not the classification used during randomization.

Primary and secondary endpoints will be tested using only three treatment groups: izokibep 160 mg Q2W, izokibep 160 mg QW and placebo. The treatment group receiving izokibep 80 mg Q4W will only be used for exploratory analyses and endpoints.

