#### 5.1.2. Screening Period

For all subjects, the screening period starts when the subject signs and dates the ICF and ends when the subject is enrolled/randomized, or screen failed. The screening period is up to 28 days. Certain initial screening period procedures may be repeated during the original initial screening period. This is not considering “rescreening”.

The baseline value for a variable is therefore defined as the last non-missing value collected before randomization.

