  - Any time during period 1 (meet Hy's Law at least one time / not meet Hy's Law at any time)
- Period 2
  - Baseline prior to period 2 (meet Hy's Law / not meet Hy's Law)
  - Any time during period 2 (meet Hy's Law at least one time / not meet Hy's Law at any time)

A listing of all liver function test results from all subjects who meet Hy's Law at least one time during the study will be produced, sorted by subject and date. This listing will show subject, treatment assignment, period, ALT, AST, ALP, bilirubin and INR.

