#### **6.7.4. Vital Signs**

The analyses described below will be conducted for the following vital signs assessments respectively:

- SBP (mmHg)
- DBP (mmHg)
- Heart Rate (bpm)
- Respiratory Rate (breaths/min)
- Body Temperature (°C)

In accordance with the baseline value definition in Section 5.1.2, the change from baseline will be derived as follows:

$$\text{Change (unit)} = (\text{post-baseline value} - \text{baseline value})$$

The following will be summarized for the Safety Analysis Set:

- Observed values and change from baseline at each assessed timepoint for each standard vital sign parameter using default summary statistics for continuous variables.

A listing of all vital signs data including derived change from baseline will be provided for the Safety Analysis Set.

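### Period 2 laboratory and vital-sign summaries for the placebo crossover group use the pre-randomization baseline, so they mix placebo-phase change with change after the first izokibep dose

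*SAP*

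**What the plan says.** SAP 5.1.2 gives one baseline for all variables: "The baseline value for a variable is therefore defined as the last non-missing value collected before randomization". Protocol 9.3.1 agrees: "Baseline values will be the last value collected before randomization".

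Unless otherwise specified, SAP 6.7 reports every safety table separately for Period 1 (the first 16 weeks) and Period 2 (after the Week 16 visit). In Period 2, Group 1 has its own column, labelled as placebo followed by izokibep QW. Under SAP 5.1.3, Period 2 starts with the Week 16 dose. SAP 2.1 makes that Group 1's first izokibep dose.

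Four summaries use the single baseline:

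- Laboratory change (SAP 6.7.3): "In accordance with the baseline value definition in Section 5.1.2, the change from baseline will be derived as follows".
- Laboratory reference-range shift (SAP 6.7.3), with categories taken "relative to the reference range at baseline compared to each post-baseline timepoint for hematology and clinical chemistry".
- Laboratory CTCAE shift (SAP 6.7.3): "Number and percentage of subjects with categorized shift NCI-CTCAE toxicity values at baseline compared to worst post-baseline result".
- Vital signs (SAP 6.7.4): "Observed values and change from baseline at each assessed timepoint for each standard vital sign parameter", with change derived "In accordance with the baseline value definition in Section 5.1.2".

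Two neighbouring analyses do reset. The Period 2 block of the Hy's Law shift table in SAP 6.7.3.1 opens with a row beginning "Baseline prior to period 2 (meet". SAP 6.7.2 counts an adverse event as emergent in Period 2 only if it starts, or worsens in severity, from the Week 16 dose onward.

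**The concern.** A separate Period 2 column for Group 1 is useful because it shows what happens once these subjects start izokibep. With a pre-randomization baseline it shows something else: the sum of 16 weeks on placebo and the time since crossover.

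The reference points also conflict within one report. Take a laboratory abnormality that arises on placebo, is reported as an adverse event and then persists unchanged. By the SAP 6.7.2 rule it is not a Period 2 treatment-emergent event, yet SAP 6.7.3 tabulates it as a Period 2 shift.

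Laboratory values and vital signs belong to a stated secondary safety objective, worded in terms of clinically significant findings. The protocol also means to keep the two phases apart for these subjects: its synopsis summarizes the last 36 weeks separately for those randomized to placebo, and section 9.3.5 summarizes their adverse events by phase.

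**Working it through.** The plan gives no figure on this point to reproduce. The check is to trace the reference point, write out what it implies, and size the effect under stated assumptions.

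**1. Reference points for Period 2**

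| Summary | Reference point | SAP section |
|---|---|---|
| Laboratory change | Last value before randomization | 6.7.3, via 5.1.2 |
| Laboratory reference-range shift | Baseline, with only 5.1.2 to define it | 6.7.3 |
| Laboratory CTCAE shift | Baseline, with only 5.1.2 to define it | 6.7.3 |
| Vital-sign change | Last value before randomization | 6.7.4, via 5.1.2 |
| Hy's Law shift | Status before Period 2 | 6.7.3.1 |
| Treatment-emergent adverse events | Week 16 dose | 6.7.2 |

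**2. What a Group 1 Period 2 change contains**

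(Period 2 value − pre-randomization value) = (Week 16 value − pre-randomization value) + (Period 2 value − Week 16 value)

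The first term on the right accrues entirely on placebo. This follows from the definitions and needs no assumption.

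**3. Illustrations with assumed ALT values (U/L)**

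- Values of 30 before randomization, 60 at Week 16 and 60 at Week 24. The SAP change is 60 − 30 = +30, and there is a shift to high if the upper limit lies between 30 and 60. From Week 16 the change is 60 − 60 = 0, with no shift.
- Values of 60, 30 and 60. The SAP change is 60 − 60 = 0, and high-to-high is no shift. From Week 16 the change is 60 − 30 = +30.

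The distortion can therefore go either way.

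**4. Possible number of subjects**

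The documents give no rate of laboratory shifts on placebo. Let p be the proportion of Group 1 (n = 100, SAP 2.1) that shifts on placebo and r the proportion of those shifts that persist. Both are assumed. The expected number is 100 × p × r. The chance of at least one such subject is 1 − (1 − p × r)^100, treating subjects as independent.

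| p | r | Expected subjects | Chance of at least one |
|---|---|---|---|
| 2% | 0.5 | 1 | 63% |
| 2% | 1 | 2 | 87% |
| 5% | 0.5 | 2.5 | 92% |
| 5% | 1 | 5 | 99% |
| 10% | 0.5 | 5 | 99% |
| 10% | 1 | 10 | > 99% |

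These counts describe carry-over alone, with no izokibep effect at all.

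**The case against.** The strongest reply is that one pre-randomization baseline for all groups is a legitimate choice. It agrees with the protocol and keeps the columns comparable at each visit. The SAP's two resets at Week 16 are not confined to Group 1, so a reset for Group 1 alone copies neither of them. This has force, and it is why the pre-randomization display should stay. It does not settle the matter: Groups 2 to 4 received izokibep from Day 1, so their pre-randomization value already precedes any drug. For Group 1 the corresponding value is the one just before the Week 16 dose.

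A second reply is that the drift is partly visible. Laboratory change, reference-range shift and vital-sign change are reported by visit, Week 16 is a listed laboratory timepoint, and the listings give every value. That stands for mean change. By-visit margins do not recover subject-level shifts, though, and a listing does not correct a summary table. The weakest spot is the CTCAE shift to the worst post-baseline grade, which has no visit structure. The general rule in SAP 6.7 suggests that the worst value in Period 2 comes from Period 2 data only, but the item itself does not say so.

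A third reply is that the most important signals are protected elsewhere. That is correct for Hy's Law and for treatment-emergent events. Protocol 8.2.8 also requires clinically significant laboratory changes to be recorded as adverse events.

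A reader might infer that the SAP counts placebo-period changes as izokibep effects. The documents do not support that. The column label states the treatment sequence, no rule assigns causality, and protocol 9.3.5 excludes p-values for safety data. Nor do they support extending the point to vital-sign shifts, because SAP 6.7.4 plans only observed values and change.

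**Conclusion.** The point holds in a limited form. Group 1's Period 2 laboratory and vital-sign changes, and its laboratory reference-range and CTCAE shifts, include the placebo phase. This is inconsistent with the SAP's own handling of Hy's Law and treatment-emergent events. The harm lies mainly in subject-level laboratory shifts, above all the worst-grade CTCAE table.

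The mixing itself follows from the definitions; its size does not. The range of about 1 to 10 subjects rests wholly on the assumed shift and persistence rates and should not be read as a prediction. Efficacy inference and the Hy's Law and adverse-event summaries are unaffected. This is a correction to how descriptive safety tables are built, not a threat to the trial's conclusions on efficacy.

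**What to change.** In SAP 6.7.3 and 6.7.4:

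- Define a Period 2 baseline for Group 1 as the last non-missing value before the Week 16 dose. Use it for that group's Period 2 laboratory and vital-sign change and for its laboratory shifts.
- State that the worst post-baseline result in Period 2 is limited to values after the Week 16 dose.
- Keep the pre-randomization baseline for Groups 2 to 4, and label the baseline used in each column.
- Retain Group 1's change from the pre-randomization baseline as an additional display, so that columns can still be compared on a common footing.

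The cost is SAP wording, one derived baseline flag, two baselines to label and a few extra table columns. No new data are needed. Week 16 laboratory values and vital signs are already scheduled, and protocol section 8 places assessments before dosing unless otherwise specified.

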#### **6.7.3.1. Liver toxicity review**

Potential liver toxicity will be assessed by listing subjects who met potential drug induced liver injury (DILI) criteria as described in the protocol and by summarizing subjects who met Hy's Law.

Subjects who met any (one or more) of the following criteria will be included in a listing for consideration of DILI:

- ALT or AST  $\geq 5 \times$  ULN at any time
- ALT or AST  $\geq 3 \times$  ULN at all (2 or more) assessments in a span of  $\geq 4$  weeks
- ALT or AST  $\geq 3 \times$  ULN and total bilirubin  $\geq 2 \times$  ULN ( $>35\%$  direct bilirubin) simultaneously at any time
- ALT or AST  $\geq 3 \times$  ULN and international normalized ratio (INR)  $\geq 1.5$  simultaneously at any time
- ALT or AST  $\geq 3 \times$  ULN at any time during the study and weekly assessments after this finding are not available for at least 4 weeks
- ALT or AST  $\geq 3 \times$  ULN associated with symptoms (new or worsening) believed to be related to liver injury or hypersensitivity at any time

To determine subjects who meet the last criterion, a listing of all subjects who have at least one ALT or AST  $\geq 3 \times$  ULN at any time, and who do not meet any of the first five criteria, will be reviewed by qualified medical professionals along with a listing of all AEs reported by such subjects. In coordination with the investigator, the medical professionals will assess whether any AE is believed to be related to liver injury or hypersensitivity and, if so, whether the elevated ALT or AST is in temporal association with the AE. Any subjects who meet these criteria will be included on a memo that will be filed in the TMF prior to database lock and unblinding, and included in the listings. For subjects who meet any of the six criteria, all liver function test results at any time during the study will be listed, sorted by subject and date. Listing will include subject, treatment assignment, ALT, AST, bilirubin and INR, along with specific criterion met.

Subjects who meet the criteria for Hy's Law will be displayed in shift tables. Hy's Law is met when ALT or AST is  $\geq 3 \times$  ULN, total bilirubin  $\geq 2 \times$  ULN and ALP is  $<2 \times$  ULN, with all occurring simultaneously (at the same draw). At each assessment, subjects will be classified as meeting Hy's Law or not meeting Hy's Law. The shift tables will be presented as follows:

- Period 1
  - Baseline (meet Hy's Law / not meet Hy's Law)
  - Any time during period 1 (meet Hy's Law at least one time / not meet Hy's Law at any time)
- Period 2
  - Baseline prior to period 2 (meet Hy's Law / not meet Hy's Law)
  - Any time during period 2 (meet Hy's Law at least one time / not meet Hy's Law at any time)

A listing of all liver function test results from all subjects who meet Hy's Law at least one time during the study will be produced, sorted by subject and date. This listing will show subject, treatment assignment, period, ALT, AST, ALP, bilirubin and INR.

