7.1. Discontinuation of Study Drug

In rare instances, it may be necessary for a subject to permanently discontinue study drug. The reason for permanent discontinuation of study drug will be documented. If study drug is prematurely and permanently discontinued, the subject will be encouraged to remain in the study to be evaluated for safety and efficacy. Subjects should continue to complete study assessments as outlined in the SoA ([Section 1.3](#)) where possible, with the exception of study drug administration, and anti-drug antibody sample and PK sample collection. Reasons for removal from study drug include any of the following:

- subject request
- death
- lost to follow-up
- termination of study by sponsor
- emergency unblinding
- liver chemistry stopping criteria (see [Section 7.1.1](#))
- serious infections
- the subject becomes pregnant while on study drug
- malignancy
- subject develops CTCAE v5.0 grade 3 or higher SAE or AE(s) that is considered by the investigator to be related to study drug
- subject develops an illness that, in the opinion of the Investigator, would interfere with his or her continued participation, if the risk of continuing with study drug outweighs the potential benefit
- subject uses prohibited concomitant medications, as defined in [Section 6.8.3](#), that may present a risk to the safety of the subject in the opinion of the Investigator or the Medical Monitor
- subject is non-compliant with TB prophylaxis (if applicable) or develops active TB at any time during the study
- subject is significantly non-compliant with study procedures which would put the subject at risk for continued participation in the trial as determined by the Investigator or Medical Monitor
- subjects with disease progression or not responding to treatment are to be withdrawn from study drug treatment based on Investigator's discretion

- Starting at Week 24, subjects who have not met clinical Disease Activity for PsA (cDAPSA) low disease activity ($cDAPSA \leq 14$) at 2 consecutive visits (e.g. at Week 20 and Week 24) will be discontinued from study drug and can receive standard of care treatment as deemed appropriate by the Investigator.

Subjects with newly diagnosed IBD during the study must:

- discontinue study drug and be followed-up until resolution of active IBD symptoms
- be referred, as appropriate, to a health care professional treating IBD, such as a gastroenterologist

[figure not shown]

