c) Considered effective, but not highly effective failure rate of $\geq 1\%$ per year.

Note: Periodic abstinence (calendar, symptothermal, postovulation methods), withdrawal (coitus interruptus), spermicides only, and lactational amenorrhea methods are not acceptable methods of contraception. Male condom and female condom should not be used together (due to risk of failure from friction).

10.5. Liver Safety: Actions and Follow-up Assessments and Study drug Restart/Rechallenge Guidelines

Phase 2 liver chemistry stopping criteria are designed to assure subject safety and to evaluate liver event etiology. The guidelines provided below are based on the EASL Clinical Practice Guidelines: Drug Induced Liver Injury (2019) and Food and Drug Administration 2009 Guidance for Industry Drug-induced Liver Injury: Premarketing Clinical Evaluation.

Phase 2 Liver Chemistry Stopping Criteria and Follow-up Assessments

Liver Chemistry Stopping Criteria	
ALT or AST-absolute	ALT or AST $\geq 5 \times$ ULN
ALT or AST Increase	ALT or AST $\geq 3 \times$ ULN persists for ≥ 4 weeks
Bilirubin^{1,2}	ALT or AST $\geq 3 \times$ ULN and total bilirubin $\geq 2 \times$ ULN ($> 35\%$ direct bilirubin)
International Normalized Ratio (INR)²	ALT or AST $\geq 3 \times$ ULN and INR > 1.5
Cannot Monitor	ALT or AST $\geq 3 \times$ ULN and cannot be monitored twice weekly for 4 weeks
Symptomatic³	ALT or AST $\geq 3 \times$ ULN associated with symptoms (new or worsening) believed to be related to liver injury or hypersensitivity
Suggested Actions, Monitoring, and Follow-up Assessments	
Actions	

 Immediately discontinue study drug. Report the event to the sponsor/designee within 24 hours. Complete a serious adverse event (SAE) eCRF if the event met the criteria for an SAE.² Perform follow-up assessments as described in the Follow-up Assessment column. Monitor the subject until liver chemistry test abnormalities resolve, stabilize, or return to baseline. 	
Follow-up Assessments	

 Viral hepatitis serology. Obtain blood samples for pharmacokinetic (PK) analysis after the most recent dose.⁴ Obtain serum creatine phosphokinase, lactate dehydrogenase, gamma glutamyl transferase, glutamate dehydrogenase, and serum albumin. Fractionate bilirubin if total bilirubin $\geq 2 \times$ ULN. 	

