
MONITORING:
 
If ALT or AST $\geq 3 \times$ ULN AND total bilirubin $\geq 2 \times$ ULN or INR > 1.5:
 
 Repeat liver chemistry tests (include ALT, AST, alkaline phosphatase, total bilirubin, and INR) and perform liver event follow-up assessments within 24 hours. Monitor subject twice weekly until liver chemistry test abnormalities resolve, stabilize, or return to baseline. A hepatology consultation is recommended. 
If ALT or AST $\geq 3 \times$ ULN AND total bilirubin $< 2 \times$ ULN and INR ≤ 1.5:
 
 Repeat liver chemistry tests (include ALT, AST, alkaline phosphatase, total bilirubin, and INR) and perform liver chemistry follow-up assessments within 24 to 72 hours. Monitor subjects twice weekly until liver chemistry abnormalities resolve, stabilize, or return to baseline, or the study drug has been discontinued; then decrease monitoring to once weekly or less. Do not restart/rechallenge subject with study drug unless allowed per-protocol and sponsor approval is granted. 	
 Obtain complete blood count with differential to assess eosinophilia. Record the appearance or worsening of clinical symptoms of liver injury, or hypersensitivity, on the eCRF. Record use of concomitant medications (including acetaminophen, herbal remedies, and other over-the-counter medications) on the concomitant medications eCRF. Record alcohol use on the liver event alcohol intake form. 
If ALT or AST $\geq 3 \times$ ULN AND total bilirubin $\geq 2 \times$ ULN or INR > 1.5 obtain the following in addition to the assessments listed above:
 
 Antinuclear antibody, anti-smooth muscle antibody, type 1 anti-liver kidney microsomal antibodies, and quantitative total immunoglobulin G or gamma globulins. Serum acetaminophen adduct assay, when available, to assess potential acetaminophen contribution to liver injury in subjects with definite or likely acetaminophen use in the preceding week. Liver imaging (ultrasound, magnetic resonance, or computerized tomography) to evaluate liver disease. Liver biopsy may be considered and discussed with local specialist if available, for instance: 
 In subjects when serology raises the possibility of autoimmune hepatitis.
---	--

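### The SAP's DILI listing claims the protocol's criteria but tests for weekly rather than twice-weekly monitoring, so one narrow kind of case is left off

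*SAP*

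**What the plan says.** SAP Section 6.7.3.1 says that potential liver toxicity will be assessed by "listing subjects who met potential drug induced liver injury (DILI) criteria as described in the protocol". Six bullets follow, and meeting any one puts a subject on the listing. The fifth covers ALT or AST at or above 3 x ULN where "weekly assessments after this finding are not available for at least 4 weeks". Subjects at or above 3 x ULN "and who do not meet any of the first five criteria, will be reviewed by qualified medical professionals", who look for a related adverse event under the sixth bullet.

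The protocol's criteria are in Section 10.5. The matching row is ALT or AST at or above 3 x ULN in a subject who "cannot be monitored twice weekly for 4 weeks". The action on meeting any criterion is "Immediately discontinue study drug". For an isolated transaminase rise, the monitoring text says "Monitor subjects twice weekly until liver chemistry abnormalities resolve, stabilize, or return to baseline". It then adds a further end point and a step-down in frequency: "or the study drug has been discontinued; then decrease monitoring to once weekly or less".

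Protocol Section 7.1 names the liver chemistry stopping criteria among the reasons for stopping study drug and adds: "The reason for permanent discontinuation of study drug will be documented".

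**The concern.** The SAP says it reproduces the protocol's criteria, then uses a different test frequency in one of them without comment. Requiring one test a week where the source requires two makes the bullet harder to meet. Some subjects who satisfy the protocol wording would not satisfy the SAP wording.

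What is at stake is the completeness of one safety listing. This listing brings together treatment assignment, all liver tests and the specific criterion met. A reader told that it follows the protocol would have no reason to look elsewhere for subjects who met the monitoring criterion.

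**Working it through.** The plan gives no figure to reproduce. The check compares the two rules and then runs test profiles through both.

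**Inputs.** The six SAP bullets (SAP 6.7.3.1), the six stopping criteria and the monitoring text (protocol 10.5), and the scheduled laboratory visits (SAP 6.7.3: baseline and Weeks 4, 8, 12, 16, 20, 24, 32, 36, 40, 52 and 59).

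**Step 1: the two rules as test counts.** Let n1 to n4 be the numbers of tests in the four weeks after the first value at or above 3 x ULN. Following the SAP, read 'cannot be monitored' as tests not being available.

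- SAP bullet met: min(n1, ..., n4) < 1.
- Protocol wording met: min(n1, ..., n4) < 2.
- Difference: min(n1, ..., n4) = 1, so every week has a test and at least one week has only one.

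If no week has more than two tests, the difference covers totals from 1+1+1+1 = 4 to 2+2+2+1 = 7 tests in 28 days. This is an outer limit. It includes subjects stepped down to weekly testing as Section 10.5 allows, for example two tests in week 1, resolution, then 1, 1, 1 (five tests). The gap is clear only where testing was weekly while ALT or AST was still raised.

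**Step 2: do the other SAP bullets catch the case?** Profiles are in multiples of ULN, with normal bilirubin and INR. Weekly tests are on days 0, 7, 14, 21 and 28.

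| Profile | Protocol wording, availability reading | SAP |
|---|---|---|
| 4.0, 3.4, 2.5, 1.5, 1.0, no symptoms | met | no bullet met |
| Same values, with liver or hypersensitivity symptoms | met | bullet 6 |
| 4.0, 3.8, 3.5, 3.3, 3.1 | met | bullet 2 (at least 3 x ULN throughout 4 weeks) |
| 4.0, 3.4, no day-14 test, 1.5, 1.0 | met | bullet 5 |
| 5.2, 3.4, 2.5, 1.5, 1.0 | met | bullet 1 (at least 5 x ULN) |
| 4.0, then twice weekly 3.8, 3.4, 2.9, 2.5, 2.0, 1.5, 1.2, 1.0, no symptoms | not met | no bullet met |

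Only the first row differs. Bullets 3 and 4 need a bilirubin or INR result. Bullet 6 needs a related, temporally associated adverse event.

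**Step 3: how much testing this takes.** The intervals between scheduled laboratory visits are 4, 4, 4, 4, 4, 4, 8, 4, 4, 12 and 7 weeks, with a minimum of 4. If the rise is found at a scheduled visit, at most one of the four weekly tests can be scheduled, so at least 4 - 1 = 3 must be unscheduled. These are conditions, not rates. The documents give no ALT or AST elevation rate.

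**Step 4: effect of the one-word change.** Any subject with min < 1 also has min < 2, so everyone the bullet now lists stays listed, and the first row is added. A clause that stopped counting at resolution would break this. Take 3.5 x ULN, normal on a day-3 retest, and no further tests (counts 1, 0, 0, 0). The current bullet lists this subject, and so does the changed word alone. With a resolution clause, the subject would drop off.

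**The case against.** The strongest counter-argument is that the protocol row is a prospective stopping rule about feasibility. A subject who could have been tested twice weekly but was tested once does not plainly meet it. A retrospective listing has to turn the rule into available data, and the protocol does not say how. This stands as a limit: the omission follows on the availability reading, which is the SAP's own. It does not explain the lower frequency, since the SAP could have used availability and kept 'twice weekly'.

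Section 10.5 also permits weekly or less frequent testing after resolution, stabilisation, return to baseline or stopping drug. A reader might therefore infer from Step 1 that every subject with a week of fewer than two tests met the protocol criterion and was lost. The documents do not support that, because many such subjects could have been monitored correctly.

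A reader might also infer that the SAP bullet is looser throughout. It is not. A week without a test puts the subject on the listing, even if testing stopped because the value had resolved.

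The practical effect is small. An omitted subject still goes to the medical review of those at or above 3 x ULN and appears in the full laboratory listings. If drug was stopped, the reason is tabulated and listed under SAP Section 6.2. An inference that stopping rules, SAE reporting or efficacy results are weakened would be wrong, since the listing governs none of them.

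Finally, the protocol's liver algorithm figure (Figure 3) is not available, so the comparison rests on the Section 10.5 text.

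**Conclusion.** Wrong as written, minor. The SAP cites the protocol's criteria and departs from them in one word, without a stated reason. The subject left off is asymptomatic, with ALT or AST 3 to below 5 x ULN, no bilirubin or INR criterion, only weekly tests through four weeks while still raised, and at least one value below 3 x ULN by day 28. The number is unknown and may be zero.

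The conclusion assumes that monitoring is judged by available tests, as the SAP does, and that the figure not shown does not alter the Section 10.5 wording. If the bullet instead means that no weekly test was done in any of the four weeks, it is narrower still, and the same subject is omitted.

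**What to change.** In the fifth bullet of SAP Section 6.7.3.1, change 'weekly' to 'twice weekly'. Add no exemption for resolution or for stopping study drug. A resolution clause would remove subjects now listed, and 'stabilise' has no definition that could be programmed. A discontinuation exemption would defeat the criterion, because meeting it requires study drug to be stopped.

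Also list any subject whose documented reason for stopping study drug is the liver chemistry stopping criteria. This covers the prospective reading: a subject stopped because twice-weekly testing was not feasible is listed however often tests were then done.

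The cost is one word and one added listing rule. Protocol Section 7.1 already requires the reason to be documented. The eCRF is not among the documents, so whether this reason is a coded field needs checking. The listing becomes slightly longer and will include some subjects properly stepped down to weekly testing. That is acceptable for a listing meant only to bring cases forward for consideration of DILI.
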